Generally, the results of exercise programs show the final changes after an intervention, leaving aside the capacity for adaptation to workload during the intervention. The processes of adaptation to exercise are studied mainly in athletes; however, little is known about the adaptability capacity, in special populations, regarding CRFs, metabolic flexibility, physical function, and non-oncologic chronic pain, specifically in users belonging to the Cardiovascular Health Program of the External CESFAM of Valdivia, subjected to two types of exercise.

Despite knowing the link between non-oncologic chronic pain and the presence of cardiovascular diseases, the individual relationship between different cardiovascular risk factors and pain intensity is still uncertain.

Thus, implementing a physical exercise program associated with the PSCV will improve the possibility of controlling CRFs, improving metabolic flexibility, reducing non-oncologic chronic pain, and promoting lifestyle change difficult to achieve in users of this cohort. On the other hand, the External CESFAM will be recognized as a pioneering establishment in the implementation of non-pharmacological alternatives (personalized and expert-guided physical exercise) to improve the health and quality of life of PSCV users, which will not generate extra costs to the establishment for its application.

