### **Inclusion and Exclusion Criteria**

Inclusion: a) Being physically inactive (not performing 300 or 150 min of moderate or vigorous intensity physical activity respectively per week measured with the IPAQ questionnaire); b) BMI between 25 and 39.9 kg/m^2; c) Belonging to the cardiovascular health program of the External CESFAM of Valdivia d) Presenting with or without non-oncologic chronic pain.

Exclusion: a) Bone disease; b) Ischemic disease or arrhythmia and c) Chronic respiratory disease d) Uncontrolled chronic diseases f) People unable to understand instructions, g) People who do not speak Spanish h) History of previous oncological disease or under study for suspected neoplastic disease in any part of the body i) Low adherence to training (< 70% or non-attendance at 4 continuous sessions).

Included users will be divided into 3 groups: HIIT, ERE, and Control. All subjects will be evaluated at four times: pre-intervention (week 0 – time 1), week 4 (time 2), week 8 (time 3), and post-intervention (week 12 – time 4). Only the evaluation of metabolic flexibility and direct oxygen consumption will be carried out pre (week 0) and post-intervention (week 12).

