### **Physical Activity Level and Quality of Life**

The international physical activity questionnaire (IPAQ) (40) will be applied to estimate the level of physical activity prior to the intervention. Health-related quality of life will be measured using the SF36 questionnaire (41) before and after the intervention.

Physical Function Physical function will be measured through the Six-Minute Walk Test, and grip dynamometry.

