## **Adaptation Capacity to Workload**

The capacity to adapt to workloads will be evaluated through the changes observed in the tests described above at four times: pre-intervention, week 4, week 8, and post-intervention (week 12).

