## **Statistical Analysis**

The sample size will be calculated as follows: (1) ANOVA for repeated measures with intra-inter-group interaction, (2) three groups, (3) type I error: 5%, (4) type II error: 20%, (5) statistical test power: 80%, and (6) effect size (ES): 0.10 according to Cohen's classification (1988). Using these parameters, the total sample size recommended by G\*Power software (Version 3.1.9.2) was 174 (58 per group). Assuming a 10% dropout, the total was calculated at 192, with 64 participants randomly assigned to each group. The concealment of allocation will be conducted by a researcher not involved in the clinical procedures of the intervention using the

method of opaque, sealed, and consecutively numbered envelopes. The random sequence and allocation concealment allow for the control of selection bias.

For enhanced bias control, the data analysis will be performed by a researcher blinded to the intervention groups. Dependent variables will be described in terms of mean and standard deviation. Assumptions of normality and homoscedasticity for all data will be verified using the Shapiro-Wilk test and the Levene's test, respectively. To address General Objective 1, the Student's t-test will be used to detect baseline differences between groups, and a repeated measures ANOVA (group x time) to determine differences in all dependent variables between training prior, and at 4, 8, and 12 weeks afterwards. The Bonferroni post hoc test will be used to test differences between groups. Additionally, the Cohen's d test will be applied to determine the effect size. To address the General Objective, the Pearson correlation test will be used to determine the relationship between MHR and the presence and intensity of non-oncological chronic pain. The level for statistical significance was set at  $p < 0.05$ . Statistical analyses will be performed using SPSS software version 21 (SPSS™ Inc., Chicago, IL, USA).

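### For four-visit outcomes, the only follow-up named after the group x time test compares groups, so the time course of adaptation and the HIIT versus ERE difference in it have no pre-specified estimate

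*Combined protocol and SAP*

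**What the plan says.** The Problem Statement faults exercise studies for reporting final changes only, "leaving aside the capacity for adaptation to workload during the intervention". The section on Adaptation Capacity to Workload sets the measure: "The capacity to adapt to workloads will be evaluated through the changes observed in the tests described above at four times". Objective 1.2 asks for a comparison of HIIT and ERE on that capacity. The schedule, under Inclusion and Exclusion Criteria, matches: "All subjects will be evaluated at four times: pre-intervention (week 0 – time 1), week 4 (time 2), week 8 (time 3), and post-intervention" at week 12.

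For General Objective 1, the Statistical Analysis section plans a baseline t-test, "a repeated measures ANOVA (group x time) to determine differences in all dependent variables" over weeks 0, 4, 8 and 12, and Cohen's d. The follow-up is one sentence: "The Bonferroni post hoc test will be used to test differences between groups". It names no visit, no change from baseline, no time contrast and no confidence interval. It also does not say to which comparison Cohen's d applies.

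Some outcomes have two visits only. On the laboratory exercise measures: "Only the evaluation of metabolic flexibility and direct oxygen consumption will be carried out pre (week 0) and post-intervention (week 12". On the SF-36: "Health-related quality of life will be measured using the SF36 questionnaire (41) before and after the intervention".

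**The concern.** With three groups and four visits, the interaction test has (3 - 1)(4 - 1) = 6 degrees of freedom. A significant result says that the group profiles are not parallel. It does not say at which visit they separate, which group moved, or by how much. That job falls to the follow-up, and the one named concerns groups only.

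In a repeated-measures ANOVA, a post hoc test on the group factor compares each group's mean over all visits. Baseline is one of those visits, and under randomisation no group difference is expected there, so it dilutes any effect. The result is one number per pair of groups, with the time dimension averaged out.

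At stake is the question that sets this trial apart. The week 4 and week 8 visits would be made, but no stated estimate would use them to describe the course. Visit-specific contrasts could still be chosen after the data are seen. With many outcomes and three follow-up visits, that freedom is what pre-specification should remove.

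**Working it through.** **Inputs from the Statistical Analysis section.** Three groups, f = 0.10, alpha 5%, power 80%, N = 174 (58 per group) before dropout. Four visits come from the schedule. **Assumed, because not stated:** correlation between visits rho = 0.5, and sphericity.

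**1. The plan's own figure.**
- Noncentrality: lambda = f² x N x m / (1 - rho) = 0.01 x 174 x 4 / 0.5 = 13.92.
- Degrees of freedom: 6 and (174 - 3) x 3 = 513.
- Power from the noncentral F: 0.804. The smallest N that reaches 80% is 173, which rounds to 174 for equal groups.
- At the same rho, three visits would need 204 and two visits 246. The stated N therefore matches the four-visit, 6-df interaction test. If sphericity fails with epsilon = 0.75, power at 174 falls to 0.71.

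**2. What the group comparison sees.** Suppose both exercise arms share a linear course against a flat control, at the planned effect size. Let D be the exercise-minus-control difference at week 12, in SD units.
- The course (0, 1/3, 2/3, 1), centred, has sum of squares 5/9. The group pattern (1, 1, 0), centred, has sum of squares 6/9.
- D = sqrt[13.92 x 0.5 / (58 x 6/9 x 5/9)] = sqrt(0.324) = 0.569.
- Difference in the four-visit mean: D x (0 + 1/3 + 2/3 + 1)/4 = 0.285, half of D.
- SD of a person's four-visit mean: sqrt[(1 + 3 rho)/4] = 0.791. SE of the difference: 0.791 x sqrt(2/58) = 0.147.
- SD of change from baseline: sqrt[2(1 - rho)] = 1.00. SE of the difference in change: sqrt(2/58) = 0.186.

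Power for one exercise-versus-control pair at alpha = 0.05/3 (critical value 2.394, normal approximation):

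| Course | D | Four-visit mean | Week-12 change |
|---|---|---|---|
| Linear | 0.569 | 0.32 | 0.75 |
| All by week 4, then held | 0.490 | 0.54 | 0.60 |
| Only at week 12 | 0.490 | 0.06 | 0.60 |

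For the two step courses, the centred sum of squares is 0.75, so D = sqrt[6.96 / (58 x 6/9 x 0.75)] = 0.490. The four-visit mean differences are then 0.75D and 0.25D. With the t distribution, the linear row reads 0.32 and 0.74. With D held at 0.569, the linear row becomes 0.43 against 0.58 at rho = 0.3, and 0.26 against 0.94 at rho = 0.7.

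**3. The pooled figure does not identify the course.** A four-visit mean difference of 0.285 SD arises from a linear rise to 0.569, from a step at week 4 of 0.285/0.75 = 0.38 that is held, or from a week-12-only difference of 0.285/0.25 = 1.14. These are three different answers to the trial's question.

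**4. Precision of visit-specific contrasts.** The 95% half-width is 1.96 x sqrt[2(1 - rho)] x sqrt(2/58). That is 0.36 SD at rho = 0.5, 0.43 at 0.3 and 0.28 at 0.7. Under the linear course at rho = 0.5, power for one exercise-versus-control change is 0.17, 0.53 and 0.87 at weeks 4, 8 and 12 without adjustment. Shared over nine contrasts (0.05/9), it is 0.04, 0.23 and 0.62. The early visits can support estimates but not adjusted tests.

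**The case against.** The strongest reply is that the planned model already holds the answer. The ANOVA sentence gives its purpose as differences between baseline and weeks 4, 8 and 12, and Bonferroni comparisons between groups can be run at each visit. This shows intent, and it rules out the inference that the model is unable to locate change. The gap is in specification: the text does not say that the comparisons are made by visit or on change from baseline. Means, SDs and Cohen's d are planned, so some description by visit is likely, but it is not tied to a contrast or an interval.

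Two other stronger readings are tempting.

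- **That the 6-df test wastes power.** It reproduces at its planned 80%. A 4-df test on linear and quadratic time would have 0.86 for a linear course, 0.85 for a plateau at week 8, and 0.83 for change complete by week 4 or seen only at week 12. It would have 0.76 for a step between weeks 4 and 8, and 0.43 for an effect at week 4 only. The documents give no expected shape, and the Problem Statement says that little is known about adaptability in such populations. Polynomial terms would also not show when change occurs.
- **That repeat-test learning would count as adaptation.** The definition speaks of changes observed, without mention of the control group. But controls attend the same four visits, and learning common to all arms falls in the time effect and cancels from the planned interaction. What stands is narrower: the definition should say that adaptation is judged between groups.

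**Conclusion.** The concern holds as a specification gap. For four-visit outcomes, no named analysis estimates the time course of adaptation or the HIIT versus ERE difference in it. The one named follow-up, read literally, averages the course away.

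Under a linear course, the named follow-up targets half the week-12 difference, with power of about 0.32 against 0.75 for the week-12 change. The gap is small for an early sustained step (0.54 against 0.60) and very large for a late one (0.06 against 0.60). These figures rest on rho = 0.5, sphericity, 58 analysed per arm, the plan's f = 0.10 and two exercise arms with equal effects. If the investigators meant Bonferroni tests at each visit, the power comparison falls away, but the need to name the contrasts remains.

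The point does not apply in this form to metabolic flexibility, oxygen consumption or the SF-36. With two visits, their interaction has (3 - 1)(2 - 1) = 2 degrees of freedom, and there is no intermediate course to describe.

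**What to change.** In Statistical Analysis, keep the group x time test as sized and replace the sentence on the group post hoc test with contrasts from the same model:

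- For four-visit outcomes, estimate change from week 0 at weeks 4, 8 and 12 for HIIT minus control, ERE minus control and HIIT minus ERE, each with a 95% CI.
- Name week 12 as the key visit and test its three pairs with Bonferroni (0.05/3 each). Report weeks 4 and 8 as estimates with intervals, without significance claims.
- For outcomes measured only at weeks 0 and 12, use the week-12 change contrasts alone.
- State that Cohen's d refers to these same contrasts.

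In Adaptation Capacity to Workload, add that adaptation is judged on these between-group differences in change.

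The cost is wording and nine contrasts per four-visit outcome, from data already planned, with no extra visits or participants. The downside is limited precision: about ±0.36 SD per contrast at rho = 0.5, so a modest week-4 difference will not be distinguished from none. A Bonferroni-adjusted week-12 interval is wider, at 2.394 x 0.186 = ±0.44 SD. The rule covers pairs within one outcome; it does not settle multiplicity across the many outcomes.

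### The group x time ANOVA uses week 0 only as a time level and fixes no visit or family for the between-group comparisons; adjusting for baseline would be more precise on the same data

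*Combined protocol and SAP*

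**What the plan says.** The main analysis in the Statistical Analysis section is a "repeated measures ANOVA (group x time) to determine differences in all dependent variables between training prior, and at 4, 8, and 12 weeks". The pre-training value is thus one of four levels of time. Its only other stated use is a preliminary check, in which a Student's "t-test will be used to detect baseline differences between groups". No baseline covariate appears anywhere.

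The between-group comparison is specified in one sentence: "The Bonferroni post hoc test will be used to test differences between groups". For effect size, a Cohen's "d test will be applied to determine the effect size". Neither sentence names a visit, a number of comparisons, or whether visit values, changes or averages over visits are compared.

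The design has three arms: "Included users will be divided into 3 groups: HIIT, ERE, and Control". Specific Objective 1.2 is the comparison of the two exercise programmes. Some outcomes are not measured four times: "Only the evaluation of metabolic flexibility and direct oxygen consumption will be carried out pre (week 0) and post-intervention (week 12"), and "Health-related quality of life will be measured using the SF36 questionnaire (41) before and after the intervention".

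**The concern.** Week 0 is recorded before training and, under randomisation, carries no treatment effect. Treating it as a further outcome level means that its information reaches the between-group comparison through change from baseline. Change subtracts the whole baseline value, whereas a covariate subtracts only the part that predicts the later value. Unless the correlation is 1, the covariate leaves less residual variance.

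The second gap concerns prespecification. An ordinary reading of the Bonferroni sentence covers all three pairs, but it leaves open whether the family is 3 contrasts (one visit) or 9 (three post-baseline visits), and on what scale they are made. At stake are the precision of the HIIT-control, ERE-control and HIIT-ERE answers, and the freedom to settle visit and family size once results are known.

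**Working it through.** **Inputs from the documents.** Three groups; visits at weeks 0, 4, 8 and 12; 5% type I error; 80% power; effect size 0.10 (read as Cohen's f); 174 evaluable, 58 per group.

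**Assumed, because the documents do not give them.** Correlation rho between week 0 and week 12 of 0.3, 0.5, 0.7 or 0.8; equal SDs at all visits; a pairwise difference of 0.5 SD at week 12; two-sided tests.

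**The plan's own figure.** For the within-between interaction, lambda = f² x N x m/(1 - rho), with 6 and 3(N - 3) df. With rho = 0.5 and m = 4, lambda = 0.01 x 174 x 4/0.5 = 13.92 on 6 and 513 df, giving power 80.4%. So rho = 0.5 reproduces 174. That makes 0.5 a sample-size input, not evidence about any outcome.

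**Pairwise contrast at week 12.** In units of SD², the per-person variance is 2(1 - rho) for change, 1 - rho² after baseline adjustment, and 1 for the week-12 value alone. The adjusted-to-change ratio is (1 + rho)/2. The standard error is the square root of 2 x variance/58.

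At rho = 0.5:
- Change: SE = sqrt(2 x 1.00/58) = 0.186 SD.
- Adjusted: SE = sqrt(2 x 0.75/58) = 0.161 SD.

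Power for 0.5 SD at alpha 0.05/3 (normal approximation), and n per arm for 80% power:

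| rho | Variance cut against change | Power, adjusted | Power, change | Power, week 12 alone | n per arm, adjusted | n per arm, change |
|---|---|---|---|---|---|---|
| 0.3 | 35% | 67% | 45% | 62% | 77 | 118 |
| 0.5 | 25% | 76% | 62% | 62% | 63 | 84 |
| 0.7 | 15% | 92% | 86% | 62% | 43 | 51 |
| 0.8 | 10% | 98% | 97% | 62% | 31 | 34 |

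Simulation (4,000 trials per setting, 3 x 58) agrees: at rho 0.5 it gives 75.0% adjusted and 61.3% on change. With no true effect, every method rejects in 1.2% to 2.0% of trials against a nominal 1.67%.

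**Family size.** At rho 0.5, a family of 9 instead of 3 lowers adjusted power from 76% to 63%.

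**Omnibus test at rho 0.5.** Take constant correlation and both exercise arms 0.5 SD above control at week 12. The squared deviations of the arm effects from their mean sum to (2/3) x 0.25 = 0.1667, so lambda = 58 x 0.1667 x q = 9.667q, where q depends on the time course and the model.

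- Planned interaction (6 df): q is the sum of squares of the time profile about its mean, divided by 1 - rho. Linear growth: 0.5556/0.5 = 1.111, lambda 10.74. Complete by week 4: 0.75/0.5 = 1.5, lambda 14.5.
- Joint baseline-adjusted group effect at weeks 4, 8 and 12 (6 df): the conditional variances are 0.75 and covariances 0.25. Linear growth: q = 0.2222/0.5 + 1.3333/1.25 = 1.511, lambda 14.61. Complete by week 4: q = 3/1.25 = 2.4, lambda 23.2.

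With the non-central chi-square, power is about 68% (linear) or 83% (complete by week 4) for the planned test, against 83% or 97% for the joint adjusted test.

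**Outcomes measured twice.** With f = 0.10 and N = 174, the two-level ANOVA has lambda = f² x N x 2/(1 - rho) on 2 and 171 df. ANCOVA multiplies lambda by 2/(1 + rho), on 2 and 170 df. At rho 0.5, lambda is 6.96 against 9.28 and power 64% against 78%. Over rho 0.3/0.5/0.7/0.8, power is 49/64/87/97% against 69/78/92/98%.

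**The case against.** The strongest reply is that this is a preference between two valid analyses. Group x time ANOVA is standard, the trial was sized for it, and it matches the stated interest in how adaptation develops during the programme. All of that stands. The gain over change also depends on an unknown correlation: it is 6 power points at rho 0.7 and 1 point at 0.8.

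Week 12 as the visit for the pairwise contrasts is a proposal. In Objective 1.2, 12 weeks is the length of the programme, not a named primary visit. The Problem Statement criticises studies that report only final change, and Adaptation Capacity to Workload refers to all four assessments. Weeks 4 and 8 must therefore stay in the report.

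Two limits on scope also stand. Under Metabolic Parameters, glucose, cholesterol and triglycerides come from routine programme tests, so a value at each visit is not assured. Users without chronic pain may enrol, so pain intensity may cluster at zero, where these variance formulas may fit poorly.

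A reader might infer more than the documents support:
- **That the planned test is biased, or that 174 is wrong.** Neither follows. The ANOVA is valid under randomisation, and 174 is reproduced.
- **That the planned test cannot see an effect complete by week 4.** That would be true of a 4-df group x time term fitted to post-baseline visits only (34% linear, 5% complete by week 4, at rho 0.5). The planned interaction includes week 0 and has 6 df.
- **That the Bonferroni comparisons will average over all four visits and so dilute the effect with week 0.** The sentence does not say so. It is one possible reading of an open specification.
- **That the twice-measured outcomes cannot be analysed as planned, or that the baseline t-test damages the results.** The same ANOVA runs with two time levels. The t-test has no stated consequence for the analysis; that it compares two groups when there are three is a wording point.

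**Conclusion.** The point holds as lost precision and incomplete prespecification. The direction is firm: for a week-12 contrast, adjustment has lower variance than change for any rho below 1, apart from one degree of freedom spent on the covariate. The size is conditional. Over rho 0.3 to 0.8 the variance falls by 35% to 10%. The corresponding power gain for an assumed 0.5 SD difference runs from about 21 points to 1. For the omnibus test at rho 0.5, the gain is about 15 points (linear growth) or 14 (complete by week 4). These figures rest on equal SDs and normal theory, and the omnibus figures also on constant correlation. The change should be made, but the trial would not be invalid without it.

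**What to change.** In Statistical Analysis:

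1. Analyse weeks 4, 8 and 12 with a linear mixed model containing baseline value, group, time, group x time and baseline x time, with unstructured covariance. The named software suffices: "Statistical analyses will be performed using SPSS software version 21", using its MIXED procedure.
2. Take as the omnibus test the joint 6-df group effect over the three post-baseline visits, not the group x time term of that model alone.
3. Name the contrasts (HIIT-control, ERE-control, HIIT-ERE), their visit and the Bonferroni family. Week 12 with three contrasts per outcome at 0.05/3 is proposed as consistent with a 12-week programme. Report weeks 4 and 8 as well, for the adaptation aim. Give Cohen's d for the same contrasts.
4. Use week-12 ANCOVA with baseline as covariate for metabolic flexibility, oxygen consumption and SF36.
5. Replace the baseline t-test with a description of baseline by group.
6. State how routine laboratory values are matched to visits and what is done when one is missing.

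This needs no new visits, participants or software. The main test would then differ from the interaction that gave 174, which must be stated, and the gain is small where rho is high. Fixing visit and family within each outcome does not address multiplicity across outcomes.

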## **Objectives**

### **General**

- Objective 1: Evaluate the effects of a 12-week HIIT and ERE program on the workload adaptation capacity in cardiometabolic risk factors, physical function, and non-oncologic chronic pain in users of the Cardiovascular Health Program at the External CESFAM of Valdivia.
- Objective 2: Determine the relationship between cardiovascular risk factors and non-oncologic chronic pain in users of the Cardiovascular Health Program at the External CESFAM of Valdivia.

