## **Specific**

- Objective 1.1: Analyze the effects of a 12-week HIIT and ERE program on the workload adaptation capacity in cardiometabolic risk factors, physical function, and non-oncologic chronic pain in users of the Cardiovascular Health Program at the External CESFAM of Valdivia.
- Objective 1.2: Compare the effects of a 12-week HIIT and ERE program on the workload adaptation capacity in cardiometabolic risk factors, physical function, and non-oncologic chronic pain in users of the Cardiovascular Health Program at the External CESFAM of Valdivia.
- Objective 2.1: Determine the relationship between the number of cardiovascular risk factors and the presence of non-oncologic chronic pain in users of the PSCV at the External CESFAM of Valdivia.
- Objective 2.2: Determine the relationship between the number of cardiovascular risk factors and the intensity of non-oncologic chronic pain in users of the PSCV at the External CESFAM of Valdivia.
- Objective 2.3: Associate the presence of non-oncologic chronic pain with other chronic diseases.

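### All dependent variables are tested at p < 0.05 with no primary outcome named in the protocol and no control across outcomes, and the sample size of 174 is attached to none of them

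*Combined protocol and SAP*

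**What the plan says.** The general objective is to evaluate "workload adaptation capacity in cardiometabolic risk factors, physical function, and non-oncologic chronic pain". These three domains are listed without ranking. Specific objective 1.2 adds a head-to-head aim: "Compare the effects of a 12-week HIIT and ERE program on the workload adaptation capacity". The section Adaptation Capacity to Workload says that this capacity "will be evaluated through the changes observed in the tests described above at four times", so the construct is change in every test and no variable leads. Expected Results does not single one out either.

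Under Statistical Analysis, a group-by-time repeated measures ANOVA is used "to determine differences in all dependent variables between training prior, and at 4, 8, and 12 weeks afterwards". Then: "The Bonferroni post hoc test will be used to test differences between groups". "The level for statistical significance was set at" p < 0.05, with no allocation across outcomes.

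The sample size in the same section uses the within-between interaction of a repeated measures ANOVA, three groups, 5% type I error, 80% power and "effect size (ES): 0.10 according to" Cohen's classification. The result is 174 (58 per group), raised to 192 for dropout. No outcome, unit, standard deviation, within-person correlation, sphericity value or number of measurements is given there.

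**The concern.** With no outcome ranked in advance, the 5% level applies to each test separately. Nothing in the plan distinguishes a result the trial was designed to show from one that crosses 0.05 by chance among many. This affects both exercise versus control and HIIT versus ERE. The Bonferroni step does not help here, because it corrects the three group pairs inside a single outcome.

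The sample size has a related weakness. A power of 80% means something only for a particular outcome with its own schedule, correlation and scale. Here f = 0.10 is a conventional value that could describe any of the variables, including some measured only twice.

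**Working it through.** **1. The plan's own figure.** Inputs from Statistical Analysis: f = 0.10, 3 groups, alpha 0.05, power 80%. Four measurements come from Inclusion and Exclusion Criteria ("All subjects will be evaluated at four times"). Within-person correlation rho = 0.5 and sphericity (epsilon = 1) are assumptions.

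The noncentrality is lambda = f² × N × m / (1 − rho), with df 2(m − 1) and (N − 3)(m − 1).

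- N = 174: lambda = 0.01 × 174 × 4 / 0.5 = 13.92, df 6 and 513, power 80.4%.
- N = 171: lambda = 13.68, power 79.6%.

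So 174 is the smallest total with equal groups that reaches 80%, and the plan's figure reproduces.

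**2. How far it depends on the unstated inputs** (N = 174, f = 0.10):

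| Measurements | rho | epsilon | Power at 174 | N for 80% |
|---|---|---|---|---|
| 4 | 0 | 1 | 46.0% | 345 |
| 4 | 0.3 | 1 | 63.5% | 243 |
| 4 | 0.5 | 1 | 80.4% | 174 |
| 4 | 0.7 | 1 | 96.8% | 105 |
| 4 | 0.5 | 0.75 | 71.1% | 210 |
| 2 | 0.5 | 1 | 64.5% | 246 |

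The size of effect that f = 0.10 implies also depends on its shape over time. If both exercise arms gain equally over control, f² = d² × (2/9) × V. Here d is the week-12 difference in change, in SDs of a single measurement, and V is the variance over the four visits of the fraction of the effect present. Linear build-up has V = 0.139, so d = 0.57 SD. Full effect from week 4, or at week 12 only, has V = 0.1875, so d = 0.49 SD. Full effect from week 8 has V = 0.25, so d = 0.42 SD.

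**3. Number of outcomes (my count).**

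- *Four times, 15 variables:* 6MWT, grip, weight, % fat, lean mass, BMI, waist, systolic and diastolic pressure, heart rate, glucose, cholesterol, triglycerides, pain intensity, pressure pain threshold.
- *Possibly only 10:* Metabolic Parameters takes the 3 laboratory values from routine programme controls, and the Work Plan for months 4 to 6 lists only cardiometabolic variables and pain, which omits 6MWT and grip. 15 − 3 − 2 = 10.
- *Before and after only, 3:* SF-36 (counted as one), metabolic flexibility, oxygen consumption.

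The total is 10 + 3 = 13 to 15 + 3 = 18.

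**4. Chance of at least one significant interaction when nothing changes.** Under independence it is 1 − 0.95^K: 40.1% (K = 10), 53.7% (15), 60.3% (18). These are upper bounds. The correlated rates come from null simulation with 3 × 58 participants, four times, within-person correlation 0.5 and a common between-outcome correlation:

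| Outcomes | Correlation 0.5 | Correlation 0.7 |
|---|---|---|
| 10 | 31% | 23% |
| 15 | 38% | 28% |
| 18 | 42% | 30% |

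The row for 18 treats every outcome as measured four times. Testing three of them at two times changes it by only about two percentage points.

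**5. Chance of a false favourable exercise-versus-control result at week 12.** Bonferroni gives two-sided 0.05/3 per pair. For one outcome, two arms can each win in the favourable direction: 2 × 0.05/6 = 1.67%, or about 1.6% after overlap. Over several outcomes the simulated rate, as correlation rises from 0 to 0.7, is 21% to 10% (15 outcomes) or 15% to 8% (10). At correlation 0 this agrees with 1 − 0.984^15 = 21.5% and 1 − 0.984^10 = 14.9%.

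If the comparison is made only after a significant interaction, the rate depends on a contrast that the plan does not state. For 15 outcomes it is about 9% to 5% on change from baseline (one outcome 0.6%), or about 3–4% falling to 2% on week-12 values (one outcome 0.2%).

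**The case against.** *The outcomes overlap, so independence exaggerates.* This stands. Weight and BMI move almost together in adults of fixed height, and fat, lean mass, waist and the two blood pressures are related. The 40%, 54% and 60% figures should not be read as the trial's error rate. Even at correlation 0.7, however, the rate is 23% to 30%.

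*The count is inferred.* True: the sections disagree or leave it open. The five variables perhaps not repeated every four weeks may still be tested before and after, which would put the total nearer 18 than 13. No plausible count brings the rate near 5%.

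*There is a multiplicity step.* There is, and it limits false claims between groups within each outcome. A reader should not infer that the plan has no correction at all. What it lacks is control across outcomes.

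*174 is correct.* A reader might infer that the sample size is wrong or that its power cannot be checked. Neither follows: it reproduces under ordinary assumptions. The gap is that those assumptions are unstated and belong to no outcome.

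*The trial is exploratory.* The documents do not say so. They randomise 192 people, state 80% power at 5% error and set a comparative objective. If exploration is intended, estimates with confidence intervals would suit it.

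A reader might also infer that no primary outcome was ever declared. These documents show only that the protocol and its analysis section name none.

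**Conclusion.** The point holds. As written, the plan carries roughly a 23% to 42% chance of at least one false interaction across 10 to 18 outcomes, for between-outcome correlations of 0.5 to 0.7. It also leaves no rule for deciding which result is the trial's answer. The false favourable rate against control at week 12, without a gate, is about 5 to 13 times that of a single outcome (8% to 21% against 1.6%). With a gate the absolute rates are lower, and they cannot be fixed until the contrast is stated.

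These figures rest on an inferred outcome count, on correlations the documents do not give, and on no true change in any outcome. The conclusion does not depend on any one value in those ranges.

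On sample size, the finding is limited to this: 174 is arithmetically sound for four measurements, correlation 0.5 and sphericity, but the 80% claim cannot be carried to an outcome chosen later unless that outcome meets those conditions.

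**What to change.** Before outcome data are analysed by group:

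1. Name one primary outcome and reconcile its measurement times across Inclusion and Exclusion Criteria, Metabolic Parameters and the Work Plan. Test its group-by-time interaction at 0.05.
2. Tie the sample-size statement to that test. Give the assumed correlation, the sphericity value, the number of measurements and f = 0.10 in that outcome's units. Keep 80% only if those inputs support it; otherwise restate the power at 174.
3. Make all other outcomes secondary, either Holm-adjusted or reported as estimates with confidence intervals and no significance claim.
4. State whether the Bonferroni comparisons follow only a significant interaction, at which weeks, and whether they use values or change from baseline.

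The cost is wording plus agreement on one outcome, but there are two real downsides. Fewer secondary outcomes will be called significant: at the first Holm step, power for f = 0.10 over four times at 174 and correlation 0.5 is about 44% with 17 secondaries or 49% with 12. The estimation option avoids that loss. The stated power may also become less favourable, and if 80% must be kept for an outcome whose inputs do not support it, N would have to rise: for example 246 before dropout for a before-and-after outcome at correlation 0.5, or 210 with four measurements and epsilon 0.75.
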